5.1.1.1 Standardizing use of local anesthesia for participating surgeons

To ensure that patients receive local anesthesia in a consistent way, all participating surgeons will undergo a training session for the technique of local injection. This will consist of practicing injection with a 50:50 mix of 1% lidocaine with epinephrine and 0.25% Marcaine into the skin at the incision site and the subcutaneous tissue down to the external oblique aponeurosis. The technique for surgical repair will be a standard Lichtenstein operation with the choice of mesh depending on the surgeon's preference. To verify that the appropriate procedure for injection of local anesthesia is being followed, the principal investigator or research assistants will observe each surgeon's first five cases and provide feedback.

5.1.1.2 Collaboration with anesthesia providers during surgery:

We have worked closely with anesthesia providers at both sites to formulate protocols for sedation during surgery. Anesthesia providers will refrain from using benzodiazepines prior to or during surgery given the known cognitive effects of that medication class on older adults. We will not otherwise mandate use of any particular agents for sedation or pain control, but expressed our preference for using propofol and fentanyl because of their short half-lives and limited side effect profile for older adults.

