5.2 Handling of Study Interventions

The medications necessary for administration of local and general anesthesia are available at the hospital from our pharmacy as part of routine care. Local anesthesia will be prepared by the surgical circulating nurse (not a member of the research team) in the operating room as is routinely done for clinical practice outside this trial.

The research assistants will be blinded to study allocation, as they will not be present during the operation and will only interact with patients before and after the operation. Due to the use of some IV medication (propofol or Precedex) for patients in the local arm, it will not necessarily be obvious postoperatively whether the patient had surgery under local or general anesthesia. Additionally, the incisions will be the same regardless of study arm and postoperative care will be identical.

Adverse reactions to any medications intraoperatively will be managed as described below.

For studies involving drugs and dietary or nutritional supplements, describe how these are to be acquired by the participating clinical sites (e.g., the pharmaceutical company will distribute the drug in bulk to the site pharmacist), and how they are to be stored, prepared, dispensed and, if applicable, how unused study products are destroyed or to be returned to the company supplying them.

Provide instructions for completing study intervention accountability records. If appropriate, reference the study Manual of Operations for detailed instructions on these issues.

For lifestyle/behavioral interventions, describe the intervention and general approach for delivering the intervention (e.g., manual describing procedures).

Note mechanisms (if any) for masking (i.e., blinding) study interventions. For example, if a placebo is being used in a drug trial, note whether it has similar color, taste, etc., as the active drug.

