5.4 Adherence Assessment

We will review all operative and anesthesia records for cases of enrolled patients to verify the type of anesthesia that is administered and whether patients who start the operation under local anesthesia undergo a conversion to general anesthesia. Research assistants will also review cases with attending surgeons at the end of each operative day to identify any deviations from protocol. Any deviation from treatment assignment will then be recorded in the research record.

Adherence to a study regimen is generally defined as the extent to which participants take medications or comply with other study requirements as prescribed by the investigators. Define adherence (e.g., at least 80% of treatment intervention pills taken, 85% of exercise sessions attended). Provide details as to how adherence to study intervention will be assessed (e.g., pill counts, electronic monitoring devices, attendance at counseling sessions) and in the section on Data Analyses (Section 9.5), describe how this information will be incorporated into the analysis of the study results.

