6.2.3 Follow-up Visits

- Visit 2 (During Surgery)
 - The second set of assessments will occur during the normal course of clinical care for inguinal hernias (this does not represent an additional study visit on top of the usual care). During the surgery, the

anesthesiologist automatically records data on the below information as part of the routine anesthesia record.

- Vital signs: maximum, minimum, and median values for systolic and diastolic blood pressure and heart rate
 - Total operating room time: the difference between the time the patient enters the operating room and the time the patient leaves the operating room
 - Time for surgery: the time from the start of the operation (skin incision) and the end of the operation (skin closure)
 - Adverse events, serious adverse events, and intraoperative complications
 - Volume of fluids administered
 - Minimum alveolar concentration of volatile anesthetic
 - Dose of local anesthesia used
- Visit 3 (After Surgery & Before Same Day Discharge)
 - Inguinal hernia repair is typically an outpatient procedure where the patient is observed for several hours to ensure that there are no immediate complications of surgery or anesthesia and that patients are able to ambulate, tolerate oral intake, and manage basic self-care with assistance from family or other caregivers. From the time the patient leaves the operating room until the time the patient leaves the hospital, we will assess the following:
 - Vital signs: We will record any episodes of hypotension (mean arterial pressure <60) or hypertension (systolic blood pressure >180 or diastolic > 110), fever (temperature >101.6 F), tachycardia (heart rate >120), or poor oxygenation (oxygen saturation on pulse oximetry <85%). This information will be obtained from the post-anesthesia care unit and stepdown unit records.
 - Delirium and cognitive assessment: we will administer a battery of tests to assess (1) cognitive function (overall and particular domains including processing, visual scanning, attention, mental set-shifting, executive function, and verbal memory) and (2) delirium risk
 - Confusion Assessment Method (short form)
 - Montreal Cognitive Assessment (5-minute version)
 - Trail Making Tests Parts A and B

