 - Time in post-anesthesia care unit: after surgery, all patients who had their operations performed under general anesthesia are observed in a unit with a nurse:patient ratio of $\leq 2:1$, similar to intensive care units. This level of nursing care is required to quickly detect immediate complications of anesthesia, including respiratory failure and hypotension. Our research assistants will use the nursing records to determine what time the patient entered the unit and what time they were transferred to the next phase in care: the step-down unit. Patients having

surgery under local anesthesia are sent directly from the operating room to the step-down unit.

- Time in step-down unit: Once general anesthesia patients meet criteria in the post-anesthesia care unit (awake, normal respiratory drive and blood pressure), they are transferred to the step-down unit. All local anesthesia patients are transferred directly to the step-down unit once their operation is complete. In this unit, patients are provided food and liquids to test their ability to tolerate oral intake. Patients also are asked to ambulate and void to ensure that they are capable of self-care and have not developed urinary retention. Our research assistants will use nursing records to identify the time of entry and departure from the step-down unit.
 - Urinary function/unplanned catheterization: research assistants will review nursing notes to determine whether patients were able to void or whether they required assistance. Our standard clinical protocol is that if patients have not urinated by 4 hours after surgery, they will undergo a bladder scan. If >200cc of urine is found in the bladder, the patients undergo in-and-out catheterization and are observed until they void again. If still unable to void, the patient has a foley catheter placed, is started on medication for prostatic hypertrophy, and arrangements are made with the urology service to undergo outpatient voiding studies and removal of the catheter within 1-2 weeks.
 - Unplanned admission: since most inguinal hernia surgeries are outpatient procedures, our nursing assistants will check the medical record the day after surgery to see if the patient was able to leave or was admitted. If admitted, we will contact the team to determine the reason for admission.
 - Adverse events and serious adverse events
- Visit 4 (48 Hours After Surgery)

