xxvii. Deep wound surgical site infection: infection that occurs within 30 days after the operation and the infection appears to be related to the operation and infection involved deep soft tissues (e.g., fascial and muscle layers) of the incision and at least one of the following:

- Purulent drainage from the deep incision but not from the organ/space component of the surgical site.
- A deep incision spontaneously dehisces or is deliberately opened by a surgeon when the patient has at least one of the following signs or symptoms: fever (> 38 C), localized pain, or tenderness, unless site is culture-negative.
- An abscess or other evidence of infection involving the deep incision is found on direct examination, during reoperation, or by histopathologic or radiologic examination.
- Diagnosis of a deep incision SSI by a surgeon or attending physician.

-Note:

- Infection that involves both superficial and deep incision sites will be categorized as deep incisional SSI.
- An organ/space SSI that drains through the incision will be categorized as a deep incisional SSI.

b. Timing: Postoperative complications will be assessed prior to discharge and at the 2 week postoperative visit. Complications will be coded as present if identified at any time between the surgery and the 2 week visit.

6) Outcome: Operative and anesthesia times

- a. Measurement: Operative time will be recorded as the difference, in minutes, between the time of skin/wound closure and the time of surgical incision. Anesthesia time will be recorded as the difference, in minutes, between the time patients exit the operating room and the time of entrance to the operating room.
- b. Timing: Anesthesia intraoperative records routinely capture all four time points necessary to calculate the above outcomes. Records are scanned into the electronic medical record on the day of surgery and this data will be entered into the research record by research assistants on the day of surgery

(once the operation is complete).

- 7) Outcome: Recovery time (time spent in the post-anesthesia care and stepdown units)

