- a. Measurement: Immediately following surgery, patients are typically transported directly to the post-anesthesia recovery unit for close monitoring by nursing staff and anesthesia faculty. Once the effects of anesthesia have diminished and patients are able to stay awake and maintain oxygenation without additional stimuli, they are transported to the stepdown unit for a period of observation to ensure they are able to ambulate and tolerate oral intake without nausea or vomiting. Time in the post-anesthesia care unit will be recorded as the difference between time of transport to the stepdown unit and the time of exit from the operating room. Time in the stepdown unit will be calculated as the difference between the time patients are discharged from the hospital (typically on the same day as surgery) and the time of transport from the post-anesthesia care unit. If patients are admitted rather than being discharged home on the same day as surgery, then stepdown time will be calculated as the difference between arrival in the inpatient or observation unit and the time of entrance to the stepdown unit. All values will be calculated in minutes.
 - b. Timing: These values will be calculated on the day of surgery by research assistants.

Table 3. Analysis of secondary (clinical outcomes)		
Outcome	Measurement	Number of items & time to completion
Quality of life	Carolinas Comfort Scale	8 items Time to completion: 1 minute
Physical function	Katz index	6 items Time to completion: 2 minutes
Cognitive function	1) Confusion Assessment Method (short form) 2) Montreal Cognitive Assessment 5-minute form 3) Trail Making Test Parts A and B	1) 4 items, time to completion 5 minutes 2) 8 items, time to completion 5 minutes 3) 2 trails, time to completion 2 minutes
Pain	Visual Analog Scale	1 item Time to completion: 10 seconds
Postoperative complications	VA Surgical Quality Improvement Program definitions	Complications outlined above Assessed by research assistants and not participants
Operative and anesthesia times	Time from anesthesia note	Assessed by research assistants and not participants

Recovery time in post-anesthesia care unit and stepdown unit	Timer by research assistant	Assessed by research assistants and not participants
--	-----------------------------	--

State and define the secondary outcome measures.

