10 DATA COLLECTION AND QUALITY ASSURANCE

10.1 Data Collection Forms

Data will be collected for each participant by a research assistant blinded to the treatment assignment. For the baseline assessment, all forms will be completed after verifying eligibility but before opening the envelope with the treatment assignment. For subsequent assessments, another research assistant not familiar with the patient’s assignment will complete all case report forms. Every case report form will be reviewed, approved, and signed by the site principal investigator and by the project principal investigator.

Case report forms will be provided for each patient and instructions for completion maintained in our Manual of Procedures, which will be given to study staff at each participating site.

Data will be entered into an online, secure REDCap database to help maintain participant confidentiality. Additionally, separate databases will be maintained with (1) participant identifying information and (2) data from case report forms, which will be labeled with the participant’s study number. After entering data into the database, the participant can only be

identified by combining the two datasets. Otherwise, all data entry is guided by the participant's study identification number.

Indicate how information will be collected for each participant and by whom. For example if a blinded observer will perform outcome assessments, state who this person will be. Describe methods for maintaining confidentiality of participant records. Refer to Manual of Procedures (MOP) for description of study forms (also called Case Report Forms).

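### Assessor blinding is stated but not protected as written: research assistants are given arm-revealing tasks that the plan does not separate from outcome rating

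*Combined protocol and SAP*

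**What the plan says.** Sections 3.6, 5.2, 9.2.1 (masking) and 10.1 all describe the research assistants as blinded, and Section 3.6 extends this to every assessment. Section 5.2 gives the main reasons. Assistants do not learn the arm in the operating room, "as they will not be present during the operation and will only interact with patients before and after the operation"; postoperative care does not differ by arm; and sedation in the local arm makes the technique less obvious afterwards.

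Sections 9.2.1 and 10.1 add a safeguard. The baseline assistant opens the envelope only after the baseline assessment, and a different assistant, unfamiliar with the assignment, sees the patient from then on. Under Section 10.1 that second assistant "will complete all case report forms".

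Elsewhere, assistants have these tasks:

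- Section 5.1.1.1: "the principal investigator or research assistants will observe each" surgeon's first five cases, to check the local injection.
- Section 5.4: "Research assistants will also review cases with attending surgeons at the end of each operative day to identify any deviations from protocol".
- Section 6.2.3, Visit 3: they take entry and exit times for the post-anesthesia and step-down units from nursing records. The same text says "All local anesthesia patients are transferred directly to the step-down unit once their operation is complete".
- Section 9.4.2: operative and anesthesia times come from the anesthesia record, and "this data will be entered into the research record by research assistants on the day of surgery". Table 3 gives the method for recovery time as "Timer by research assistant".

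The Visit 2 data in Section 6.2.3 also include "Minimum alveolar concentration of volatile anesthetic" and the local anesthetic dose. No abstractor is named for either.

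**The concern.** The reasons given for blinding do not agree with the duties assigned. An assistant who watches an injection, discusses the day's cases with the surgeon, or finds no post-anesthesia unit entry for a patient can learn the arm. If that assistant also rates the patient, the rating is not blinded.

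This matters most where the assistant's conduct or judgment can move the result: the Confusion Assessment Method, the Montreal Cognitive Assessment, the Trail Making Tests, and adverse events elicited by questioning, for which relationship to study arm is also recorded (7.2.1). Section 9.1.5 expects cognition and complications to favor local anesthesia, so the rater's expectation has a direction. Section 9.1.3 plans to take preliminary effect sizes from these data. Testing the study procedures is itself an objective of the pilot, so a blinding procedure that does not work would be carried into the larger trial.

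**Working it through.** The plan gives no figure for this point, so the check is mainly a comparison of sections.

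1. **Absence from the operation (5.2) against 5.1.1.1.** Observation is by the principal investigator or assistants, so an assistant may be present. Section 10.3.1.1 states another rule: the principal investigator only, for each surgeon's first local operation. The number of surgeons is not given. If all five observed cases were local-arm trial cases, and an assistant attended each, 2, 4 or 8 surgeons would give 5 × 2 = 10, 5 × 4 = 20 or 5 × 8 = 40 of the 40 local cases. That is an upper bound on this route.

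2. **Absence from the operation (5.2) against 5.4.** The daily review sits in a section about which anesthetic was given and whether local was converted to general. It is hard to hold that discussion without learning the arm.

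3. **Same care in both arms (5.2) against 6.2.3.** Under 6.2.3, general-anesthesia patients pass through the post-anesthesia unit and local patients do not, so the unit-entry field shows the arm. Section 9.4.2 describes passage through that unit as typical, without distinguishing arms. The three sections do not agree.

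4. **Does the second assistant cure this?** The handover removes knowledge gained from the envelope. Section 10.1 then gives this assistant all later forms, with no exception for unit times or volatile concentration. No section creates a separate unblinded abstractor.

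5. **Timing.** The debrief is at the end of the day, and operative times are entered after surgery. Visit 3 testing, before discharge, may precede both. Knowledge from these routes would more plausibly affect the 48-hour, 2-week and 6-month assessments, if the same assistant returns.

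6. **Illustration of scale, on assumed shifts.** Suppose unblinded rating moves a score by b = 0.1, 0.2 or 0.3 SD in favor of local anesthesia. These values are assumptions. With 40 per arm, SE = √(2/40) = 0.224 SD. For a two-sided 5% z-test with no true difference, the rejection rate is Φ(−1.96 + b/SE) + Φ(−1.96 − b/SE):
   - b = 0.1: b/SE = 0.447, rate 7.3%
   - b = 0.2: b/SE = 0.894, rate 14.5%
   - b = 0.3: b/SE = 1.342, rate 26.9%

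   The planned test is the Wilcoxon rank-sum (9.5.2), so these are approximate. The effect on planning is more relevant to a pilot. Required sample size varies as 1/d². If the true difference were 0.5 SD (the plan's minimal important difference for several scales) and the next trial were sized on the biased estimate, it would have (0.5/0.6)² = 69%, (0.5/0.7)² = 51% or (0.5/0.8)² = 39% of the patients it needs.

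**The case against.** The strongest reply is that the plan does protect the rater. Sections 9.2.1 and 10.1 require a different assistant who does not know the assignment. Read strictly, Section 10.1 bars anyone who has learned a patient's arm from completing that patient's forms. The arm-revealing tasks are given to research assistants in general, not to the rater by name. Observation may fall to the principal investigator alone, and nobody is named to abstract volatile concentration or local dose. Local dose may not even separate the arms, because the plan never says that general-anesthesia patients receive no infiltration. The clinical comparisons are exploratory and the primary outcomes are feasibility measures.

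Much of this stands. A reader might infer that assessor blinding fails, or that all 80 participants will be rated by someone who knows their arm. The documents do not support that: they do not show that the person who learns the arm is the person who rates, and the observation route covers only some cases.

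The reply does not remove the defect. A requirement that the assistant be unfamiliar with the arm cannot be reliably met when the same sentence hands that assistant every later form, including those that disclose it, and nobody else is assigned them.

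**Conclusion.** The point holds as a gap in protection: the plan states assessor blinding and does not secure it. The contradictions between 5.2 and Sections 5.1.1.1, 5.4 and 6.2.3 are in the text and need no assumption. That an assessor will actually be unblinded does rest on assumptions: that assistants share the abstraction, debrief and rating tasks, and that Section 10.1 is followed literally.

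The feasibility outcomes do not depend on it. At risk are the exploratory effect estimates for delirium, cognition and elicited adverse events. The size of any bias cannot be derived from the documents, and the percentages above show only what assumed shifts would do. Patient-reported pain and quality of life, and function as reported by the patient, would not be fully protected even by perfect assessor blinding, because Section 9.2.1 accepts that patients know their arm. The change should be made before enrollment.

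**What to change.** Set fixed roles at each site, using the two assistants per patient already implied by 9.2.1 and 10.1.

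- **Unblinded assistant:** enrollment, baseline, envelope, anesthesia-record and recovery-time abstraction, surgeon debriefs and any case observation. This person rates no post-baseline outcome for any participant. A split made patient by patient is not enough, because the daily debrief covers every case of the day.
- **Blinded assessor:** post-baseline instruments only. Arm-revealing fields go on a separate form, restricted until database lock.
- **Patients:** ask them not to tell the assessor which anesthetic they had. State that patient-reported pain, function and quality of life are not blinded.
- **Text:** reconcile 5.1.1.1 with 10.3.1.1 on who observes and how many cases. Reconcile the statement in 5.2 that care is the same with the recovery pathways in 6.2.3 and 9.4.2. Align 5.4, 10.1 and Table 3 (timer against nursing records). Section 10.1 has the site and project principal investigators sign every case report form, which must be squared with the blinding claimed for investigators in 9.2.1.

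The cost is a reallocation of tasks, a form-permission setting and less flexibility in scheduling. Staffing per site is not stated. If a site cannot keep two assistants in separate roles, including cover for absence, it would need more help.
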